## **8.10 Overall Survival**

OS is defined as time from the first day of treatment to the date of death. A subject alive at the end of study or lost to follow-up will be censored for OS at the last date when the subject was known to be alive.

The median and quartiles of OS and their 95% CIs will be assessed using the Kaplan-Meier method and Brookmeyer and Crowley (1982) method, respectively. The proportion of subjects alive at 12, 24, 48, 72, 96 weeks and other timepoints of interest and associated 95% CI will be estimated using the Kaplan-Meier method. Summary of OS will be provided for the All Treated population for solid tumors and lymphoma, respectively, if data warrants.

## **8.11 Statistical Considerations**

### **8.11.1 Adjustments for Covariates**

There are no adjustments for covariates in this study.

### **8.11.2 Handling of Dropouts or Missing Data**

For the efficacy variables no imputations will be made for missing values except as noted in considering a NE response.

### **8.11.3 Interim Analysis and Data Monitoring**

No interim analyses for this study.

### **8.11.4 Multiple Comparison/Multiplicity**

No adjustments for multiplicity will be made in this study.

### **8.11.5 Multicenter Studies**

There are no planned analyses to compare differences in response by center.

## **9. PHARMACOKINETIC AND PHARMACODYNAMIC ANALYSES**

Separate analysis plans will be provided for PK and PD data.

## **10. IMMUNOGENICITY ANALYSES**

Anti-drug antibodies (ADA) data will be listed and summarized as appropriate.

## 11. SAFETY ANALYSES

Unless specified otherwise, all safety analyses will be based on the All Treated population. Safety analyses will include MTD evaluation, AEs, laboratory test results (hematology, chemistry, coagulation, thyroid), vital signs and Eastern Cooperative Oncology Group (ECOG).

### 11.1 Maximum Tolerated Dose Evaluation

The MTD evaluation will be based on the DLT Evaluable Population. The number and percentage of subjects with DLT during the dose escalation phase will be presented by dose level and schedule. The MTD level will be indicated in the summary as appropriate. For single subject cohorts, qualifying  $\geq$  Grade 2 toxicities that trigger a change to at least 3 subject cohorts will also be specified in the table footnotes.

The MTD will be estimated using isotonic regression (based on the DLTs observed in the DLT evaluable subjects). A MAD will be reported if a schedule is fully evaluated, but the DLT rate is less than 25% for all dose levels. Otherwise, an MTD will be reported. Isotonic regression is a way to estimate the MTD under the assumption that toxicity increases with dose. When using isotonic regression, the first step is to identify the doses where the dose-toxicity monotonicity assumption is violated. The DLT estimate is then adjusted for the violators such that the final estimate of the DLT rate increases with the dose. The target DLT rate is then used to select the MTD. For example, suppose that when the trial is completed, the observed DLT rates [<# subjects who experienced DLT]/[# evaluable subjects] at five dose levels are (0/3, 1/3, 0/3, 4/15, 2/4). In this example the observed DLT rate at Dose Level 2 (i.e., 1/3=33%) is higher than the observed DLT rate at Dose Level 3 (i.e., 0/3=0%). To adjust for this violation, the DLT estimates are replaced with their average, i.e.,  $(1/3+0/3)/2=1/6$ , resulting in the isotonic regression DLT estimates (0/3, 1/6, 1/6, 4/15, 2/4) = (0%, 16.7%, 16.7%, 26.7%, 50%), which monotonically increases with the dose level. Based on this isotonic estimate, assuming that the trial goal is to find the dose with the DLT rate of 30%, Dose Level 4 will be selected as the MTD. If there are no violators of the dose-toxicity monotonicity assumption, isotonic regression directly uses the observed DLT rates as the final estimates for MTD selection. For subjects who undergo intra-subject dose escalation, only DLTs that occur during the DLT period on the subject's initial dose will be used for MTD determination.

In the case of dose levels with estimated toxicity of equal distance (tied dose levels) from the target toxicity of 30%, the following approach will be used: among all tied dose levels the highest dose level with target toxicity  $\leq$  30% will be selected, unless all tied dose levels have estimated toxicity  $>$  30%, in which case the lowest dose level will be selected.

### 11.2 Adverse Events

AE terms on the eCRFs will be mapped to preferred terms (PT) and system organ classes (SOC) using the Medical Dictionary for Regulatory Activities (MedDRA) Version 26.0.

Drug-related AEs are defined as AEs with relationship to study treatment being related or possible related. A worst-case scenario approach will be taken to handle missing data, i.e. AEs with missing relationship to study drug will be treated as drug-related AEs.

All AEs with onset dates on or after the first dose of study treatment are defined as treatment-emergent adverse events (TEAEs). Only TEAEs will be included in AE tables.

If both the start and end dates are completely missing, the AE will be considered treatment-emergent. Partial start and end dates will be imputed similarly as described for prior and concomitant medications in Section 7.7 for the purpose of determining treatment-emergent and AE duration.

The AE summaries that are displayed by SOC and PT will be ordered by descending order of incidence of SOC and PT within each SOC based on the total number of subjects. The following summaries will be presented.

- Overall Summary of TEAEs.
- Subject incidence of all TEAEs, drug-related TEAEs, immune related TEAEs by MedDRA SOC, PT and maximum toxicity grade. At each level of subject summarization, a subject is classified to the highest toxicity grade if the subject reported one or more events.
- Subject incidence of all TEAEs, serious TEAE, drug-related TEAEs, and drug-related serious TEAEs by PT.
- Subject incidence of all TEAEs with toxicity grade 3 or 4 by PT.
- DLT for dose escalation cohorts.
- Subject incidence of all TEAEs leading to drug interruptions and permanent discontinuation of study treatment by PT.
- Subject incidence of immune related TEAEs leading to permanent discontinuation of study treatment by PT.
- Subject incidence of deaths within and outside of 30 days of last dose and cause of death.

All AEs, immune related AEs (irAEs), immune related SAEs (irSAEs), drug-related AEs, Grade 3 or 4 AEs, drug-related Grade 3 or 4 AEs, DLTs for dose escalation cohorts, SAEs, fatal AEs, AEs leading to drug interrupted, dose reduced, or drug withdrawal, infusion related reaction signs and symptoms and death will be presented in data listings. Pretreatment AE, defined as AEs that start prior to the first dose of the study treatment, will be flagged in relevant listings. AEs for the Screen Failures population will also be presented in a data listing.

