Tumor Biopsy ^q	X							X										
Survival																	X	

Abbreviations: Txt = Treatment; w/in = within; C = Cycle; D = Day

- a. **Screening:** Screening Period extends from Day -21 to Day -1. The following screening assessments must be performed within 72 hours of the first dose of SL-279252: hematology profile, chemistry profile, coagulation profile, pregnancy test. Baseline CT or positron emission tomography (PET)/CT or MRI tumor assessments are required for all subjects within 28 days prior to enrollment. Subjects will be enrolled based on local PD-L1 tumor testing results. Any PD-L1 tumor testing results prior to enrollment are acceptable.
- b. **Assessment Window:** A physical exam, weight and ECOG performance status obtained for a subject within 24 hours prior to dosing on Cycle 1, Day 1 is acceptable. With the exception of Screening assessments and unless otherwise specified, assessments performed at \leq 3-week intervals will have a +/- 3-day window and assessments performed at $>$ 3-week intervals will have a +/- 1-week window. Assessments throughout the study are calendar based starting from the first day of dosing (day 1) in the first treatment period. Dose interruptions should not alter the assessment schedule for any subsequent treatment period.
- c. **Inclusion/Exclusion criteria:** Subjects must meet eligibility criteria prior to first dose of SL-279252 on C1D1.
- d. **Vital Signs:** Blood pressure (BP), heart rate (HR), temperature (T) and respiratory rate (RR) must be measured after the subject has been sitting for at least five minutes (min). Pulse oximetry will be collected to coincide with vital sign time points noted below.
 - 1) **Collect vital signs/pulse oximetry during Cycle 1 on D1, D8, D15 and C2D1:** Predose (within 30 min of starting the infusion) and 15 min (\pm 5 min), 0.5 hour [hr] (\pm 5 min), 1 hr (\pm 10 min), 1.5 hr (\pm 10 min) 2 hr (\pm 10 min), 4 hr (\pm 10 min), and 6 hr (\pm 10 min) **after SOI**.
 - 2) **Vital signs/pulse oximetry should be taken once prior to scheduled PK samples on C1D2, C1D3, C1D4, C1D5, C1D16 and C2D2**
 - 3) **Collect vital signs/pulse oximetry on dosing days \geq C2D15:** Predose (within 30 min of starting the infusion) and at the end of infusion [EOI] (\pm 2 min)

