7. SAFETY ASSESSMENTS

Subjects will be followed continuously for AEs starting when a subject has signed the ICF, throughout the course of treatment and for 90 days after the last dose of IP. After a subject is discontinued from SL-279252 due to progressive disease or for other reasons, any ongoing AEs should be followed until resolution (or return to baseline) and documented in the eCRF. If another anti-cancer agent is started within 90 days after the last dose of SL-279252, only SAEs and AEs that occur prior to starting the new anticancer therapy should be recorded. All observed or volunteered AEs (serious or non-serious) and abnormal laboratory test findings, if applicable, whether suspected to have a causal relationship to the SL-279252 or not will be recorded in the subject medical record and in the eCRF. AEs will be graded according to NCI-CTCAE v5.0. For all AEs, sufficient information will be pursued and/or obtained to permit an adequate determination of seriousness and outcome of the event (i.e., whether it should be classified as a SAE or not) and an assessment of the causal relationship between the AE and SL-279252. AEs will be followed until resolution (or return to baseline) or stabilization. Refer to Section 7.5 for documentation and reporting of AEs.

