7.2 Definitions for Safety Parameters

Event	Definition
Adverse Event (AE)	The AE observation period starts at the time of signing informed consent and includes baseline or washout periods, even if no study treatment has been administered. AE is any untoward medical occurrence in a subject to whom the IP has been administered, regardless of whether the event is considered related to that product. An AE is also an undesirable medical condition due to a study-related procedure.
Adverse Reaction (AR)	AR is an untoward and unintended response in a subject to an IP. A causal relationship between a trial medication and an AE is at least a reasonable possibility, i.e. the relationship cannot be ruled out.
Serious Adverse	An AE or suspected AR that is considered "serious" if, in the view of either the investigator or Sponsor, it results in any of the following outcomes:

Event	Definition
Event (SAE) or Serious Adverse Reaction (SAR)	
 Death (Note: death is an outcome not an event) A life-threatening AE (an event in which the subject was at risk of death at the time of the event; it does not refer to an event which hypothetically might have caused death if it were more severe) Inpatient hospitalization or prolongation of existing hospitalization A persistent or significant incapacity or substantial disruption of the ability to conduct normal life functions A congenital anomaly/birth defect. Important medical events that may not result in death, be life-threatening, or require hospitalization may be considered serious when, based upon appropriate medical judgment, they may jeopardize the participant and may require medical or surgical intervention to prevent one of the outcomes listed in this definition. Examples of such medical events include allergic bronchospasm requiring intensive treatment in an emergency room or at home, blood dyscrasias or convulsions that do not result in inpatient hospitalization, or the development of drug dependency or drug abuse.

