### **7.7 Prior and Concomitant Medications**

Verbatim terms on electronic case report forms (eCRFs) will be mapped to Anatomical Therapeutic Chemical (ATC) class and Generic Drug Names using the World Health Organization (WHO) Drug Dictionary Global B3 format, September 1, 2018 release.

Prior medications are defined as medications that end prior to the date of the first dose of study treatment. Concomitant medications are defined as medications taken on or after the date of the first dose of study drug. Any medications that started prior to the date of the first dose but continued beyond the date of first dose will be counted as concomitant medications.

If both the start and end dates are completely missing, the medication will be considered concomitant. For cases where start or end dates are partially recorded, the following imputation algorithms will be used for the purpose of determining prior or concomitant medications:

- Missing start day, but month and year present:

If year and month are same as first dosing year and month, assign the day of first dosing date to the partial date. Otherwise, assign 1st of the month to the partial date.

- Missing start day and month, but year present:

If year is same as first dosing year, assign the month and day of first dosing date to the partial date. Otherwise, assign January 1st to the partial date.

- Missing end day, but month and year present:

If year and month are same as end of study participation year and month, assign the day of end of study participation to the partial date. Otherwise, assign the last day of the month to the partial date.

- Missing end day and month, but year present:

If year is same as end of study participation year, assign the month and day of end of study participation date to the partial date. Otherwise, assign December 31st to the partial date.

If the study is ongoing (e.g. interim analysis) and the study end date is not available, the cut-off date will be used instead.

Prior and concomitant medications along with dose, route, start/end date, and indication for each medication will be presented in a data listing.

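### The SAP defines treatment-emergent AEs by onset date alone, so an AE that starts in screening and worsens on SL-279252 can drop out of the AE incidence tables

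*SAP*

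**What the plan says.** SAP 11.2 gives the definition: "All AEs with onset dates on or after the first dose of study treatment are defined as treatment-emergent adverse events (TEAEs"). It then limits the tables: "Only TEAEs will be included in AE tables". AEs that start earlier are handled separately: "Pretreatment AE, defined as AEs that start prior to the first dose of the study treatment, will be flagged in relevant listings". Neither SAP 11.2 nor any other SAP section has a clause for worsening, and SAP section 12 lists no change on this point.

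Two date rules widen the definition slightly. One is for missing dates: "If both the start and end dates are completely missing, the AE will be considered treatment-emergent". The other is the partial-date rule of SAP 7.7, which 11.2 applies to AEs: "If year and month are same as first dosing year and month, assign the day of first dosing date to the partial date".

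On collection, protocol section 7 states: "Subjects will be followed continuously for AEs starting when a subject has signed the ICF". Protocol 7.2 agrees: "The AE observation period starts at the time of signing informed consent and includes baseline or washout periods". Footnote a of the schedule in protocol 6.1 sets the window: "Screening Period extends from Day -21 to Day -1".

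On recording, protocol 7.5 lists the description, onset and end dates, severity, relatedness and action taken. Protocol 7.4 asks for the highest grade of each AE, and for onset and duration by episode only when the AE is intermittent.

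**The concern.** AE incidence is a primary outcome of both the escalation and the expansion part. A first-in-human safety table should show toxicity that appears on drug and also toxicity that gets worse on drug. A definition that looks only at onset captures the first kind. It captures the second only if the data system turns the worsening into a new event.

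The missing clause can only lower the count of on-treatment toxicity. The two date rules quoted above may raise counts, but they act on records with missing or partial dates and do not bring back the lost event. SAP 11.3 and 11.5 summarise laboratory values and ECOG status as worst shift from baseline, so clinical AEs are the weaker case within the same plan.

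**Working it through.** The SAP states no figure to reproduce, so the check follows one event through the rules and then counts the tables.

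**1. Can an AE start before first dose?** Yes. Collection begins at consent and screening runs from Day -21 to Day -1. The SAP expects such AEs, because it plans a flag for them.

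**2. What does the record hold?** Under protocol 7.4 and 7.5: one onset date, one end date and the highest grade. Take a hypothetical continuous AE that is Grade 1 from Day -5 and Grade 3 from Day 10. Kept as one record, it reads: onset Day -5, Grade 3.

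**3. How does SAP 11.2 classify it?** Day -5 is before first dose, so it is not a TEAE. It is left out of the TEAE tables and flagged as pretreatment in the listings. Had the worsening opened a second record with onset Day 10, that record would count.

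**4. Does the protocol require a second record?** Three places bear on this.
- Protocol 7.4 treats a condition present at screening as baseline and records its deterioration after consent as an AE.
- Protocol 7.2.1 records worsening of a condition already known at trial entry. Protocol 4.4 implies that entry comes after consent, so the two together could support a new record.
- Protocol 7.4 asks for onset by episode for intermittent AEs only.

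None of these clearly covers a continuous AE already recorded after consent.

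**5. Which tables are affected?** SAP 14.1 lists 14 tables numbered 14.3.1.2 to 14.3.1.15. Two are not limited to TEAEs: 14.3.1.11 (DLTs) and 14.3.1.15 (deaths). The rule governs the other 14 - 2 = 12. One event is missing only from the tables it would qualify for:

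| Example event (single record, pre-dose onset, worse on drug) | Tables 14.3.1.x | Count |
|---|---|---|
| Unrelated, non-serious, Grade 2, no action taken | .2, .3, .6 | 3 |
| Drug-related, non-serious, not immune-related, Grade 3, interruption | .2, .3, .4, .6, .8, .10, .12 | 7 |
| Drug-related, immune-related, serious, Grade 3-4, withdrawal | .2 to .10, .13, .14 | 9 + 2 = 11 |

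The last example reaches 12 only if an interruption (.12) is also recorded for it.

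**6. How far does a row move?** By at most 1/n per affected subject, and by 0 if that subject already counts in the row.
- Expansion cohort, n = 15: 1/15 = 6.7 percentage points
- n = 6: 1/6 = 16.7 points
- n = 3: 1/3 = 33.3 points
- All escalation subjects at the planned maxima, n = 42 to 63: 1/42 = 2.4 to 1/63 = 1.6 points

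**The case against.** The strongest reply is that the effect depends on eCRF completion rules that are not in the documents. If sites open a new record on worsening, nothing is lost. Protocol 7.4 can be read to treat a condition arising in screening as baseline, so that its deterioration becomes a new AE, and protocol 7.2.1 read with 4.4 points the same way. This stands as a condition on the finding, but the protocol text does not settle it.

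Second, protocol 7.3.1 allows an AE to be judged not related when there is no temporal link between drug and onset, and a single record with pre-dose onset fits that wording. With that coding the 7-table example loses .4 and .8 and falls to 5, and the 11-table example loses .4, .8 and .9 and falls to 8. This is fair. The larger counts assume drug-related coding, which other criteria in 7.3.1 still allow.

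Third, the affected group is narrow. The AE must start after consent, be continuous and ongoing at first dose, worsen on drug, and have a start date that resolves to before dosing. For immune-related tables it is narrower still, because inclusion criterion 12 requires AEs from prior immunotherapy to have resolved, with stated exceptions. Counting tables also counts the same event repeatedly. All of this stands and bears on how often the gap matters.

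Fourth, the event is still listed. That helps less than it seems: with one onset date and only the highest grade required, the listing need not show that the grade rose after dosing.

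**Conclusion.** The concern holds. As written, SAP 11.2 leaves a continuous AE that starts between consent and first dose, and worsens on SL-279252, out of each TEAE table whose criterion it meets, provided that it is kept as one record.

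The rule reaches 12 of the 14 tables. The example events lose 3, 7 or 11, and the last two counts assume drug-related coding. Each affected subject moves a row by at most 1/n. The number of such events cannot be derived from the documents, and none is assumed here.

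The DLT and Deaths tables, the laboratory and ECOG shift tables, dose escalation and the expansion stopping boundaries are not affected. The correction should be made, but it does not threaten the design. Confidence is medium because the eCRF rules are not available.

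**What to change.** In SAP 11.2, define a TEAE as an AE with onset on or after first dose, or with onset before first dose and an increase in grade on or after first dose. Limit the pretreatment flag to AEs that start before first dose and do not worsen after it.

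The SAP wording is not enough alone, because the highest grade does not show when it was reached. Sites should therefore enter worsening of a pre-dose AE as a new dated record. AEs already entered with onset in screening and ongoing at first dose should be queried for the date of any grade increase.

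The cost is two sentences in the SAP, a CRF completion note, minor programming and site queries. The query load depends on how many such AEs exist, which the documents do not say. Some AE counts may rise. No new patients or procedures are needed.

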### 5.2.3 Study Day, Duration, and Time from Event

The reference date for age calculation is the date of consent form signed as age is an eligibility requirement. The reference date for safety, efficacy and other data analyses is the date of the first dose.

- **Study Day** – Study Day 1 is defined as the date of the first dose; the day before the first dose is defined as Study Day -1. There is no study day 0. For a given event date, Study Day is calculated relative to the date of the first dose of study drug.

Study Day = [Event Date – First Dose Date] (in days) + 1 day,  
where the event date is on or after the first dose date.

Study Day = [Event Date – First Dose Date] (in days),  
where the event date is before the first dose date.

- **Duration (Days)** – A duration is calculated as the stop date minus the start date plus one.

Duration (days) = [Stop Date – Start Date] (in days) + 1 day.

- **Time since an event** - Time since an event (e.g. time since initial diagnosis) is calculated as the reference date minus the event date. For time since initial diagnosis, the reference date is the first dose of study treatment.

- **Time to an event** - Time to an event (e.g. time to response, PFS, OS) is calculated as the event date minus the reference date+1. For time to response, PFS and OS, the first dose of study treatment is the reference date.

To convert days to months, divide the number of days by 30.4375 (365.25/12) and round to one decimal place.

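### Read literally, the SAP's AE date imputation makes some AEs that ended before first dose treatment-emergent, because SAP 11.2 has no end-date check

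*SAP*

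**What the plan says.** SAP 11.2 (Adverse Events) takes over the medication imputation: "Partial start and end dates will be imputed similarly as described for prior and concomitant medications in Section 7.7". It gives two uses for the result: "for the purpose of determining treatment-emergent and AE duration".

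The start-date rules in SAP 7.7 (Prior and Concomitant Medications) are:
- Day missing: "If year and month are same as first dosing year and month, assign the day of first dosing date to the partial date".
- Day and month missing: "If year is same as first dosing year, assign the month and day of first dosing date to the partial date".

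Neither rule refers to the end date.

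The classifications that use these dates differ. For medications: "Prior medications are defined as medications that end prior to the date of the first dose of study treatment". For AEs: "All AEs with onset dates on or after the first dose of study treatment are defined as treatment-emergent adverse events". SAP 11.2 restricts the AE tables to treatment-emergent events. It defines pretreatment AEs as those starting before first dose and flags them in listings.

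SAP 5.2.3 gives the duration formula: "A duration is calculated as the stop date minus the start date plus one". SAP 5.2.4 generally keeps imputed dates out of duration variables except where the SAP specifies otherwise, and SAP 11.2 does so for AE duration.

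Protocol Section 7 starts AE collection at consent, and the schedule of assessments places screening on Day -21 to Day -1. An AE can therefore begin and end before any drug is given.

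**The concern.** The start rule in SAP 7.7 is harmless where it was written. Moving a medication's start to the dosing date cannot change whether it counts as prior, because the end date decides that. SAP 11.2 borrows the rule for a classification that runs on the start date and does not bring an end-date test with it.

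An event known to be over before exposure can then enter the AE tables. If its causality field is blank, SAP 11.2 also counts it as drug-related. AE incidence belongs to the primary safety outcome, and SAP 5.1 presents tables by schedule and dose level, where numbers are small. Single-subject cohorts are allowed at dose levels 1 to 5, with at least 3 subjects from dose level 6.

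**Working it through.** The plan states no figure to reproduce. The check applies the written rules to dates.

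**Rules used**
- Imputed onset = first-dose date, if the partial start falls in the dosing month, or in the dosing year with the month missing (SAP 7.7).
- Treatment-emergent if onset is on or after first dose (SAP 11.2).
- Duration = stop − start + 1 (SAP 5.2.3).

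**General result.** If the AE ended b days before first dose and its onset is moved to first dose, duration = −b + 1 = 1 − b. This is 0 for an AE ending on Day -1 and negative for any earlier end. Over Day -21 to Day -1 it runs from 1 − 21 = −20 to 1 − 1 = 0. Onset equals the first-dose date every time, so every such AE is classed as treatment-emergent.

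**Worked cases, assumed first dose 22 March 2021**

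| Recorded start | Recorded end | Imputed onset | TEAE | Duration (days) |
|---|---|---|---|---|
| day unknown, March 2021 | 10 March | 22 March | yes | 10 − 22 + 1 = −11 |
| only 2021 known | 10 March | 22 March | yes | 10 − 22 + 1 = −11 |
| day unknown, March 2021 | 21 March (Day -1) | 22 March | yes | 21 − 22 + 1 = 0 |
| day unknown, March 2021 | day unknown, March (imputed 31 March) | 22 March | yes | 31 − 22 + 1 = 10 |
| day unknown, February 2021 | 10 March | 1 February | no | 38 |

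The first three rows are wrong. The fourth is a reasonable default, because nothing shows that the event ended before dosing. The fifth shows that the fault needs a partial start in the dosing month, or a year-only start in the dosing year.

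**An imputed end date can do the same.** Assume first dose on 10 March 2021, start known only as 2021, and end known only as February 2021. The end is imputed to 28 February (participation ending later) and the onset to 10 March. The AE is treatment-emergent, with duration −10 + 1 = −9.

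**Enumeration.** Take every first-dose date in 2021, with an AE ending on Day -21 to Day -1 within the dosing month and the start day unknown. Of 4893 date combinations, all 4893 are classed as treatment-emergent; 4540 have a negative duration and 353 a duration of 0 (4540 + 353 = 4893). This shows that the rule behaves uniformly. It says nothing about how often such dates occur.

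**Size in a table row.** One subject is 1/1 = 100 percentage points at a single-subject level and 1/3 = 33 points at a three-subject level. Either shift appears only if that subject has no other TEAE counted in the row.

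**The case against.** The strongest reply is that an end-date check is implied. SAP 11.2 imputes end dates as well as start dates to settle treatment-emergence, which would be pointless if onset alone decided it. It makes an AE treatment-emergent by default only when both dates are wholly missing. It also says the imputation is done similarly, not identically, and the borrowed section classes medications by end date. This is good evidence of what was meant. But no end-date rule appears in SAP 11.2, 7.7 or 5.2.4, and the written TEAE definition gives the end date no role, so a programmer following the text would produce the result above.

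The second reply is rarity, and it stands. Under Protocol 7.4 a condition present at screening is baseline, not an AE, unless it worsens. Protocol 7.5 has onset and end dates recorded, and Protocol 14.2 has discrepancies checked before database lock. The event must begin and end in a short window and still have an incomplete start date at lock.

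The third reply is that little depends on it, and most of this stands too. No AE-duration table is planned. Listings show dates as recorded, so a reader would see the pre-dose end date. An event with no temporal relationship to drug fits the not-related category in Protocol 7.3.1. The large percentage shifts reflect cohort size more than this rule.

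A worst-case defense, that uncertain timing should count against the drug, does not cover these cases: the end date already places the event before exposure.

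**Conclusion.** The point holds as a drafting fault with a small effect. On the literal text, an AE with an end date before first dose and a partial start in the dosing month (or a year-only start in the dosing year) becomes treatment-emergent, loses its pretreatment flag and has a zero or negative duration. This assumes that no unwritten end-date check is programmed and that the start date is still incomplete at analysis.

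Three stronger readings might be inferred, and the documents support none of them:
- **That the primary safety results would be materially distorted.** The documents give no frequency of partial AE dates. The protocol outcome is incidence of all AEs; restricting tables to TEAEs is the SAP's reporting convention.
- **That one event necessarily moves a dose-level incidence by 33 to 100 points.** That needs a level of one to three subjects and no other TEAE for that subject in the row.
- **That dose decisions are affected.** Escalation and the MTD rest on DLTs in the first 21 or 28 days of treatment, not on TEAE tables.

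It is worth correcting because the rule gives a wrong answer where the right one is known.

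**What to change.** Add to SAP 11.2, after the imputation sentence:

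> If the recorded or imputed AE end date is before the first dose date, the AE is not treatment-emergent. If the imputed start date would be later than the end date, impute the start as the later of the first day of the known month (or year) and the informed consent date, and never later than the end date.

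The second sentence is needed because barring a late start without naming a replacement leaves the duration undefined. With first dose on 22 March 2021 and an assumed consent date of 5 March, the AE ending 10 March gets onset 5 March, not treatment-emergent, duration 10 − 5 + 1 = 6 days. The AE ending 21 March gets duration 21 − 5 + 1 = 17 days.

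The cost is two sentences in the SAP and a small change to the AE derivation code. No added data are needed, and events of uncertain timing still count as treatment-emergent.
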